10.8.2 Independent Data Monitoring Committee

No independent data monitoring committee will be established for this study.

10.8.3 Other Committees

No other committees will be established for this study.

10.9 Termination or Suspension of the Study

10.9.1 Termination or Suspension of the Entire Study

The sponsor may prematurely terminate or suspend the study at any time for the following reasons:

- Ensuring safety of the study is difficult due to safety concerns (eg, occurrence of many treatment-related SAEs)
- Achieving the purpose of the study is considered impossible (eg, interim data suggesting lack of safety, inadequate recruitment of subjects)

If the study is prematurely terminated or suspended, the sponsor should promptly inform the investigators. The investigator or subinvestigator should promptly inform the participating subjects and change the study drug to other appropriate therapy(ies).

For withdrawal criteria for individual subjects, see [Section 4.5](#).

10.9.2 Termination or Suspension of the Study by Study Site

The investigator may prematurely terminate or suspend the study in the study site with agreement of the sponsor at any time when the investigator considers that ensuring safety of the study is difficult due to safety concerns (eg, occurrence of many SAEs).

The sponsor may request the investigator to prematurely terminate or suspend the study in the study site at any time when major violations/deviations of protocol, other procedures, and ICH GCP were not improved.

If the study site is prematurely terminated or suspended from the study, the investigator or subinvestigator should promptly inform the corresponding IRB and participating subjects and change the study treatment to other appropriate therapy(ies).

10.10 Protocol Modifications and Deviations

The investigator will conduct the study in compliance with the protocol provided by the sponsor and approval/favorable opinion given by the IRB and the regulatory authority(ies). Modifications to the protocol should not be performed without agreement of both the investigator and the sponsor. Changes to the protocol will require written IRB approval/favorable opinion prior to implementation, except when the modification is needed to eliminate an immediate hazard(s) to subjects or for other inevitable medical reasons.

The investigator or subinvestigator should document any deviation from the protocol and the reason. If the investigator deviates from the protocol or makes a change to the protocol to eliminate an immediate hazard(s) to subjects, the record should be immediately submitted to the sponsor, the study site, and the IRB by the investigator and any deviations or modifications require expedited review and approval by the IRB. After the investigator obtained approval/favorable opinion from the IRB, the investigator should obtain a written agreement of the sponsor.

When deviation from the protocol is required to eliminate immediate hazard(s) to subjects or for other inevitable medical reasons, the investigator will contact the sponsor, if circumstances permit, to discuss the planned course of action. Any deviations from the

protocol must be fully documented on source documentation. All protocol deviations will be collected and reported.

10.11 Data Management

The sponsor or designee will be responsible for data management. Procedures will be specified in documents including but not limited to the Data Management Plan.

10.12 Retention of Data

The study documents must be maintained as specified in the ICH GCP and as required by the applicable regulatory requirements. The investigator and study site should take measures to prevent these documents from being accidentally or prematurely damaged.

If the sponsor is granted manufacturing and marketing approval for the drug, the sponsor will promptly notify the head of the study site in writing.

Records will be retained for the longest of the following periods:

- At least 2 years after the last marketing application approval
- Two years after formal discontinuation of the clinical development of the investigational product
- Other period according to applicable local laws, regulations, and other regulatory requirements, whichever is latest

However, the duration of retention may be prolonged in accordance with an agreement with the sponsor. If the investigator withdraws from the responsibility of keeping the study records, custody must be transferred to an appropriate person willing to accept the responsibility.

10.13 Quality Control and Assurance

The sponsor or designee will implement and maintain quality control and quality assurance procedures with written SOPs to ensure that the study is conducted and data are generated, documented, and reported in compliance with the protocol, ICH GCP, and applicable regulatory requirements.

This study will be conducted in accordance with the provisions of the Declaration of Helsinki and all revisions thereof; in accordance with the ICH GCP and as required by the applicable regulatory requirements.

Training necessary for the study will be provided to investigators and study site personnel prior to the initiation of the study.

10.14 Publication and Disclosure Policy

All information regarding cefiderocol supplied by the sponsor to the investigator is privileged and confidential. The investigator agrees to use this information to accomplish

the study and must not use it for other purposes without consent from the sponsor. It is understood that there is an obligation to provide the sponsor with complete data obtained during the study. The information obtained from the clinical trial will be used toward the development of cefiderocol and may be disclosed to regulatory authority(ies), other investigators, corporate partners, or consultants as required.

The sponsor will retain ownership of all data. All proposed publications based on the study will be subject to the sponsor's approval requirements.

The key design elements of this protocol may be posted in a publicly accessible database(s), eg, ClinicalTrials.gov, European registries, and the Japan Pharmaceutical Information Center Clinical Trial Information (JAPIC CTI).

10.15 Financial Disclosure

The information on financial disclosure for investigators will be addressed in a separate agreement between the sponsor and the investigator.

Appendix 1 Time and Events Schedule

Hour	Screening ^a Day -2 to -1	Treatment Period											EOS Visit ^b
		Day 1			Day 2			Day 3			EOT ^k		
		Predose ^c	0	8	16	24	32	40	48	56		64	
Administrative Procedures													
Informed consent	X												
Inclusion/exclusion criteria	X												
Medical history	X												
Demographics and baseline characteristics	X												
Review of prior and concomitant medications	X	-----X											
Clinical Procedures													
Physical examination	X ^d	X ^e	X ^e	X ^e	X ^e	X ^e	X ^e	X ^e	X ^e	X ^e	X ^e	X ^e	X
Vital sign measurements ^f	X	X	X	X	X	X	X	X	X	X	X	X	X
Chest X-ray ^g	X		X	X	X	X	X	X	X	X	X	X	X
Clinical laboratory tests ^h	X		X	X	X	X	X	X	X	X	X	X	X
Creatinine clearance (to adjust cefiderocol dose) ⁱ	X	X	X	X	X	X	X	X	X	X	X	X	X
Pregnancy test ^j	X												
Adverse event monitoring ^l	X	-----X											
Study Treatments													
Administration of study drug ^m			X	X	X	X	X	X	X	X	X	X	X

AE = adverse event; eCRF = electronic case report form; EOS = End of Study; EOT = End of Treatment; SAE = serious adverse event

PK and urea sampling details and time points are described in Appendix 2.

- a Screening will occur within 48 hours prior to the administration of the first dose of cefiderocol.
- b The EOS visit will occur 7 days (\pm 3 days) after administration of the last dose of cefiderocol. The EOS visit can be performed on-site or by telephone.
- c Predose assessments will occur within 24 hours prior to the administration of the first dose of cefiderocol; if Screening occurs < 24 hours prior to administration of the first dose of cefiderocol then predose assessments do not need to be performed.
- d A complete physical examination, including measurement of body weight and height, will be performed at Screening only.

-
- e A symptom-driven physical examination relevant to the subject's current condition will be performed as part of routine patient care and at the investigator's discretion from predose (if applicable), through the first dose of cefiderocol, during administration of cefiderocol, and until the last dose of cefiderocol.
 - f Blood pressure (systolic/diastolic), body temperature, pulse rate, and respiratory rate will be measured at Screening and at least 3 times a day at approximately evenly spaced intervals across the 24-hour day, starting on Day 1 of the infusions and continuing while the subject is receiving cefiderocol.
 - g Data from chest X-rays performed as part of routine patient care will be collected at Screening and throughout the study in accordance with routine patient care; any chest X-ray taken within 48 hours of randomization can be considered as Screening (or baseline) chest X-ray. A computed tomography scan can be a substitute of chest X-ray if taken according to local standard of care.
 - h Data from clinical laboratory tests performed as part of routine patient care will be collected at Screening and from the first dose of cefiderocol, during administration of cefiderocol, and until the last dose of cefiderocol. Clinical laboratory tests during the treatment period will be symptom-driven and at the investigator's discretion. If a microbiology test has been performed to confirm the clinical diagnosis (before or during Screening), the results should be recorded in the source documents and the eCRF.
 - i Creatinine clearance must be calculated at Screening and daily during treatment period to determine cefiderocol dose.
 - j Female subjects of childbearing potential only.
 - k EOT assessments will occur within 24 hours after administration of the last dose of cefiderocol or at early termination.
 - l If an SAE is observed it must be reported to Safety and all SAEs, regardless of causality, will be followed until resolution, stabilization, the condition becomes chronic, or the subject is lost to follow-up. The investigator will make an effort to collect AEs for 7 days after the last dose of study drug.
 - m Multiple doses of cefiderocol administered as an intravenous infusion over 3 hours, every 8 hours (q8h), or every 6 hours (q6h) if augmented renal function, beginning on Day 1 and continuing for an expected minimum of 3 doses and up to a total of 6 doses in subjects with normal or augmented renal function and subjects with mild or moderate renal impairment and for an expected minimum of 6 doses and up to a total of 9 doses in subjects with severe renal impairment. Dose adjustments will be made based on renal function according to dosing recommendations per protocol. Dosing scheme of q6h is not illustrated in the Schedule of Events Table as it is expected to a rare situation.

Appendix 2 PK and Urea Samples

Bronchoalveolar lavage procedure will be conducted after the 3rd dose (or 6th dose for severe renal impairment subjects). If it is not convenient for the subject or the institution to perform the BAL procedure after the 3rd dose (or 6th dose for severe renal impairment subjects), the 4th, 5th, or 6th dose may be considered as the timing for the BAL procedure (or the 7th, 8th, or 9th dose for severe renal impairment subjects). A total of 4 blood samples for determination of plasma cefiderocol concentrations will be collected at prespecified time points after the dose at which the ELF sample is collected. Part of the ELF sample will be analyzed for urea.

PK data (both blood and ELF) will be evaluated by Sponsor for every 3 subjects to determine if modifications of the ELF sampling time point in subsequent subjects are needed (see [Figure 7-3](#)). The CRO will inform study sites upon evaluation of ELF sampling time point, which scenario and BAL time point to follow. Study sites must confirm receipt of the email.

A blood sample collection for urea analysis will be performed within 30 minutes prior to the start of the BAL procedure. Within 30 minutes prior to the start of the BAL procedure, the following ventilator parameters will be captured: respiratory rate (breaths/minute) and PEEP. Blood sample collections for pharmacokinetic analysis will be performed after the same dose as the ELF sample collection at: (1) 1 hour after the start of infusion, (2) 3 hours after the start of infusion (within 30 minutes prior to the end of infusion), (3) 2 hours after the end of infusion (within ± 1 hour), and (4) 4 hours after the end of infusion (within ± 1 hour).

Blood and ELF samples will be obtained from each subject following the time points in one of the 3 scenarios listed in the tables below:

	3rd dose of cefiderocol (or subsequent dose) ^a			
	1 hr after start of infusion	3 hrs after start of infusion	2 hrs after end of infusion	4 hrs after end of infusion
Plasma PK	X	X	X	X
Serum Urea ^b		X		
BAL PK and Urea		X		

BAL = bronchoalveolar lavage; hrs = hour(s); PK= pharmacokinetic

	3rd dose of cefiderocol (or subsequent dose) ^a			
	1 hr after start of infusion	3 hrs after start of infusion	2 hrs after end of infusion	4 hrs after end of infusion
Plasma PK	X	X	X	X
Serum Urea ^b			X	
BAL PK and Urea			X	

BAL = bronchoalveolar lavage; hrs = hour(s); PK= pharmacokinetic

Scenario 3: The next set of subjects enrolled (3 additional) will undergo BAL procedure 4 hours after the end of infusion as well as plasma PK and urea assessments in ELF and serum

	3rd dose of cefiderocol (or subsequent dose) ^a			
	1 hr after start of infusion	3 hrs after start of infusion	2 hrs after end of infusion	4 hrs after end of infusion
Plasma PK	X	X	X	X
Serum Urea ^b				X
BAL PK and Urea				X

BAL = bronchoalveolar lavage; hrs = hour(s); PK= pharmacokinetic

After the third scenario, sponsor may decide to enroll up to nine additional subjects and the timing of the BAL procedure will be determined based on the information collected from the initial 9 subjects (Scenario 1-3).

*a) 6th dose for subjects with severe renal impairment

*b) A blood sample collection for urea together with PK analysis will be performed within 30 minutes prior to the start of the BAL procedure

PK results (blood and ELF) will be reviewed by Sponsor promptly after the first 3 subjects to determine if modifications of the ELF sampling time need to be adjusted for subsequent subjects enrolled. The CRO (Syneos Health) will inform the investigator and research staff of any sampling time adjustments promptly after the sponsor review and determination. The investigator will be required to confirm receipt of the adjustment information via email or other written document as appropriate.

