1. INTRODUCTION

1.1 Rationale of Study

The primary purpose of the current study is to estimate the degree of penetration of cefiderocol into infected lung tissue in hospitalized subjects with known or suspected bacterial pneumonia who are being mechanically ventilated. The lung penetration is considered as a surrogate pharmacodynamic (PD) marker for characterizing the effect of antibiotics on bacterial pneumonia. However, β -lactam antibiotics, including cephalosporins such as cefiderocol, have demonstrated a high degree of variability and varying degrees of penetration into the lung tissue (range: 30% to 100%), despite proven efficacy and wide-spread use of these agents to treat bacterial pneumonia [1]. Even with this limitation, evaluation of lung penetration is a generally recommended method for estimating investigational antibiotic efficacy. The concentration of cefiderocol in epithelial lining fluid (ELF) will be measured at steady state at up to 3 post infusion time points and compared with a corresponding concentration of cefiderocol in plasma to estimate the concentration in ELF to plasma ratio ($R_{C,EP}$), representing the % penetration of cefiderocol into infected lung tissue. Each individual will contribute to one time point, and overall up to 18 subjects (a minimum of 3 subjects) are planned to be assessed in this study. The data from this study along with modeling and simulations will support the potential efficacy of cefiderocol in subjects with known or suspected bacterial nosocomial pneumonia due to Gram-negative bacteria.

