3.2 Rationale for Study Design and Control Group

This study is an open-label, multicenter, single-arm study and is being conducted to estimate the degree of penetration of cefiderocol into infected lung tissue, as measured by plasma and ELF cefiderocol concentrations.

The study will be conducted in an open-label (unblinded) manner considering that the primary purpose of the study is focused on PK parameter assessments, which are objective rather than subjective endpoints and therefore do not require blinding for unbiased interpretation. Accordingly, no control group is necessary to achieve the study objectives.

The 2-g dose (or renally-adjusted dose) of cefiderocol infused intravenously over 3 hours, selected for the proposed study is the anticipated therapeutic dose of cefiderocol. Furthermore, 3 doses of cefiderocol in subjects with normal or augmented renal function and subjects with mild or moderate renal impairment, and 6 doses of cefiderocol in subjects with severe renal impairment will be administered in order to achieve steady state at the time the primary study assessments are performed. The recommended blood sampling scheme for determination of plasma cefiderocol concentrations provides a collection interval that will allow the PK profiles for cefiderocol to be adequately characterized. The ELF sample, along with a blood sample, will initially be obtained at the time point where cefiderocol is expected to achieve C_{max} .

The study population consists of subjects with known or suspected bacterial pneumonia. Currently, the available concentration data for cefiderocol in ELF, a surrogate for lung tissue penetration, is in healthy subjects where approximately 24% plasma unbound concentrations were measured in ELF. However, the ELF data determined in healthy subjects may not be representative of the degree of penetration in patients with infected

lungs due to a variety of considerations including alterations in blood flow and degree of penetrability resulting from thickened secretions.

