7.5.1 Plasma Samples

A total of 4 blood samples for determination of plasma cefiderocol concentrations will be collected at prespecified time points after administration of at least 3 doses of cefiderocol in subjects with normal or augmented renal function and subjects with mild or moderate renal impairment, and after administration of at least 6 doses of cefiderocol in subjects with severe renal impairment: (1) 1 hour after the start of infusion, (2) 3 hours after the start of infusion (within 30 minutes prior to the end of infusion), (3) 2 hours after the end of infusion (within \pm 1 hour), and (4) 4 hours after the end of infusion (within \pm 1 hour). The plasma PK samples will be collected at time points around the same cefiderocol infusion that the BAL procedure is performed. A blood sample for urea assessment will be collected as part of plasma sample collection within 30 minutes prior to the BAL procedure.

For each blood sample collected, the actual sampling time will be recorded in the source documents and the eCRF.

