7.6.4.1.3 Serum and ELF Sample Collection for Urea Analysis

A blood sample will be collected for urea analysis from each subject prior to and within 30 minutes to the start of the BAL procedure.

The ELF sample collected from the BAL procedure will be used for urea analysis.

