7.8 Allowable Time Window

Measurements will be performed according to the Time and Events Schedule in [Appendix 1](#), and the acceptable time deviations relative to the time points are specified in [Table 7-2](#) below. Every effort should be made to adhere as closely as possible to procedure time points specified.

Table 7-2 Allowable Time Window

Study Activity	Specified Time or Day	Acceptable Time Window
Blood sample collection at 1 hour after the start of infusion for PK		± 15 minutes
ELF and blood sample collection at 3 hours after the start of infusion for PK		Within 30 minutes prior to the end of infusion
ELF and blood sample collection at 2 hours or 4 hours after the end of infusion for PK		± 1 hour
Blood sample collection corresponding with ELF sample collection for PK		± 5 minutes after ELF sample collection
Safety assessments		± 1 hour
EOT assessments	24 hours after the last dose of cefiderocol	+ 1 day
EOS visit	7 days after the last dose of cefiderocol	± 3 days

ELF = epithelial lining fluid; EOS = End of Study; EOT = End of Treatment; PK = pharmacokinetic(s)

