6.4. Visit Windows

Visits specified in the electronic case report form (eCRF) will be used for this study.

Measurements will be performed according to the Time and Events Schedule in protocol Appendix 1. The acceptable time deviations relative to the time points specified in Appendix 1 are shown in Table 5. Every effort should be made to adhere as closely as possible to procedure time points specified.

Table 5 Allowable Time Window

Study Activity	Specified Time or Day	Acceptable Time Window
Blood sample collection at 1 hour after the start of infusion for PK		± 15 minutes
ELF and blood sample collection at 3 hours after the start of infusion for PK		Within 30 minutes prior to the end of infusion
ELF and blood sample collection at 2 hours or 4 hours after the end of infusion for PK		± 1 hour
Blood sample collection corresponding with ELF sample collection for PK		± 5 minutes after ELF sample collection
Safety assessments		± 1 hour
EOT assessments	24 hours after the last dose of cefiderocol	+ 1 day
EOS visit	7 days after the last dose of cefiderocol	± 3 days

ELF = epithelial lining fluid; EOS = End of Study; EOT = End of Treatment; PK = pharmacokinetic(s)

Unscheduled visits after first dose of study drug will not be included in by-visit summary tables, unless otherwise specified. Data from unscheduled visits will be included in listings. If multiple records exist at the same visit/time-point, the latest record will be used for the purpose of summary tables.

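### Protocol Appendix 2 footnote b, read with Section 7.5.1, can be taken to put the plasma sample paired with ELF up to 30 minutes before BAL, while Protocol Table 7-2 and SAP Table 5 require 5 minutes, with an unclear direction

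*Protocol*

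**What the plan says.** **The 30-minute rule.** Protocol Appendix 2, footnote b: "A blood sample collection for urea together with PK analysis will be performed within 30 minutes prior to the start of the BAL procedure". Section 7.5.1 also ties the urea blood to the plasma draw: "A blood sample for urea assessment will be collected as part of plasma sample collection within 30 minutes prior to the BAL procedure". Two other places give the 30 minutes for urea and do not mention PK. Section 7.6.4.1.3 reads "A blood sample will be collected for urea analysis from each subject prior to and within 30 minutes", and the body of Appendix 2 reads "A blood sample collection for urea analysis will be performed within 30 minutes prior to the start of the BAL procedure".

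**The 5-minute rule.** Protocol Table 7-2 (Section 7.8) and SAP Table 5 (Section 6.4) have a row for "Blood sample collection corresponding with ELF sample collection for PK". In both, the permitted window is a plus-or-minus sign followed by "5 minutes after ELF sample collection".

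**The wider rows.** The same tables allow plus or minus 1 hour for ELF and blood at 2 h or 4 h after the infusion. At the 3-hour point, both must fall in the last 30 minutes of the infusion.

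**The use of the sample.** The ratio of ELF to plasma concentration (R below) is a primary objective. SAP Sections 8.3 and 8.4.2 divide the ELF value by time-matched plasma and summarise R by nominal time.

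**The concern.** Only the 5-minute row ties the denominator of R to the moment of the lavage. A site that takes footnote b at its word can draw one blood sample for urea and PK 20 minutes before BAL and believe that it has followed the schedule. At 2 h or 4 h after infusion, a draw 30 minutes before a BAL done at the nominal time still meets the 1-hour row. At the 3-hour point, blood at 2.5 h and BAL at 3 h both meet their own row.

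The SAP does not say which window makes a pair time matched, or what happens to R when the 5-minute row is missed. Section 8.4.1 allows samples far outside the sampling windows to be left out of summaries, but does not say which row counts.

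Footnote b describes early draws only. Plasma rises during the infusion and falls after it, so an early draw makes R too high at end of infusion and too low later. At a given time point the error always has the same sign, so adding subjects does not average it out.

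**Working it through.** The plan gives no figure to reproduce: no sample size calculation was made and no inferential test is planned. The check has two parts.

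**1. Do the windows agree?** Take BAL start and ELF collection as one moment, time 0, because the documents give no lavage duration.
- Footnote b with Section 7.5.1: -30 to 0 minutes.
- The 5-minute row read as plus or minus: -5 to +5 minutes. The overlap is -5 to 0.
- The 5-minute row read literally as after: 0 to +5 minutes. No draw before BAL meets it.

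A draw more than 5 and up to 30 minutes before BAL therefore meets the first rule and fails the second on either reading.

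**2. How large is the effect on R?** Inputs: half-life 2.75 h (Protocol Section 1.5.1, Phase 1 data); 3-hour infusion every 8 hours (Table 3-1). Assumptions: one compartment, steady state, ELF concentration unchanged over the gap.

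The factor on R is C(t)/C(t - gap), where t is the BAL time from start of infusion.

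- k = ln 2 / 2.75 = 0.2521 per hour.
- After the infusion, the factor is exp(-k × gap). For 15 minutes: exp(-0.0630) = 0.939. For 30 minutes: exp(-0.1260) = 0.882.
- During the infusion, in units of infusion rate over clearance, C(t) = 1 - (1 - C0) × exp(-kt), with C0 = (1 - exp(-3k)) × exp(-5k) / (1 - exp(-8k)) = 0.5305 × 0.2836 / 0.8669 = 0.1736.
- C(2.5) = 1 - 0.8264 × 0.5325 = 0.5599. C(2.75) = 1 - 0.8264 × 0.5000 = 0.5868. C(3) = 1 - 0.8264 × 0.4695 = 0.6120.
- For 15 minutes: 0.6120 / 0.5868 = 1.043. For 30 minutes: 0.6120 / 0.5599 = 1.093.

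| Blood drawn before BAL | Factor on R, BAL at end of infusion | Factor on R, BAL 2 h or 4 h after it |
|---|---|---|
| 5 min | 1.014 | 0.979 |
| 15 min | 1.043 | 0.939 |
| 30 min | 1.093 | 0.882 |

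**Sensitivity.** The half-life comes from Phase 1, not from ventilated patients. For assumed half-lives of 2 to 10 h, the 30-minute factors run from 1.093 to 1.047 at end of infusion and from 0.841 to 0.966 after it. With dosing every 6 hours and a half-life of 2.75 h, the 30-minute factor at end of infusion is 1.067. If the lavage took an assumed 10 to 15 minutes, blood drawn 30 minutes before BAL start would be 40 to 45 minutes before ELF collection, and the factor after infusion would be 0.845 to 0.828.

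**The case against.** The strongest reply is that the 30 minutes were meant for urea alone. Marker b sits on the serum urea row and the plasma PK row has no marker. Section 7.6.4.1.3 and the Appendix 2 body speak of urea only. Section 3.2 pairs the samples closely ("The ELF sample, along with a blood sample, will initially be obtained at the time point where cefiderocol is expected"), and Section 1.1 has ELF "compared with a corresponding concentration of cefiderocol in plasma". I accept this as the likely intent. It does not remove the conflict, because footnote b names PK, Section 7.5.1 makes the urea blood part of the plasma collection, and neither document says which rule prevails.

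A reader might infer that the plan simply permits a PK draw 30 minutes early. It does not. The 5-minute row still applies, and such a draw misses it.

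A reader might also take 9% or 12% as the expected error. These are limits. The 9% needs blood at exactly 2.5 h and BAL at exactly 3 h, because both must fall in the last 30 minutes of the infusion. The mid-window values of about 4% and 6% are a fairer guide. They are small beside the 30% to 100% range of lung penetration that Section 1.1 gives for β-lactams.

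The SAP also offers more transparency than the conflict suggests. Section 8.4.2 already lists individual plasma and ELF collection times and plots concentrations and R against actual times, so each gap can be worked out. Section 8.4.1 has window exclusions decided before database lock. What is missing is the rule that says which gaps matter.

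Finally, sampling details are left to laboratory manuals that I have not seen, and these may have given sites a clear instruction. The Protocol's own windows should agree all the same.

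**Conclusion.** The conflict is in the current text and touches the denominator of a primary measure. Under the stated model, a draw 15 minutes early shifts R by about +4% at end of infusion and -6% at 2 h and 4 h after it. The maxima for a 30-minute gap are about +9% and -12%. The bias is possible rather than shown, modest, and in one direction at each time point. The sizes rest on a one-compartment steady-state model, the Phase 1 half-life, dosing every 8 hours, a constant ELF concentration over the gap, and a lavage of negligible duration. The conflict between the windows on a draw well before BAL does not depend on the model.

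A reader might infer that the timing error could change the adaptive choice of sampling time. The visible text does not support that. SAP Section 3.3 bases the first step on ELF concentrations and names R only for the later step, and the schematic in Protocol Figure 7-3 is not visible here.

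This should be fixed, because it settles when the denominator sample is drawn and which pairs count. It is not a threat to the study.

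**What to change.** 1. In Appendix 2 footnote b, delete the words that join PK analysis to urea, and align the sentence in Section 7.5.1, so that the 30-minute window covers urea only.
2. Have the sponsor state one unambiguous 5-minute window in Protocol Table 7-2 and SAP Table 5. It should give the direction (either side, or after only) and the anchor (BAL start or ELF collection). The documents do not show which was meant, so the choice is the sponsor's.
3. In SAP Sections 8.3 and 8.4.2, define time matched by that row. Flag pairs outside it, using the collection times already listed, and keep all values as observed. A summary of R with and without flagged pairs is optional: with about 3 subjects per step, dropping one leaves two.

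The cost is small wording changes in both documents and one flag. It may not be free of extra sampling. If the lavage takes longer than the window, blood drawn before BAL cannot serve both urea and PK, and a separate PK draw at ELF collection may be needed.
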